## 5.2.3. Method of Assigning Subjects to Treatment Groups

The CRU will generate the randomization code for each cohort with a computer program according to the study design, the number of subjects and the treatment to be administered. Once generated, the randomization code will be final and will not be modified.

Subjects enrolled in the SAD sentinel groups will be randomized 1:1 to receive SBP-9330 or matching placebo while the rest of the subjects in the cohort will be randomized 5:1 to receive SBP-9330 or matching placebo. Subjects enrolled in the MAD and Smoker cohorts will be randomized 8:2 to receive SBP-9330 or matching placebo.

Subjects who sign the informed consent form (ICF) and are randomized but do not receive the study treatment may be replaced. Subjects who sign the ICF, are randomized and received at least 1 dose of the study treatment, and are withdrawn prematurely from the study, may be replaced by an equal number of newly enrolled subjects. A new unique randomization number

Altasciences Project Number: CNO-P5-319

will be assigned to the replacement subject. The replacement list will be provided and will be identical to the original randomization scheme.

# 5.2.4. Blinding

This study is double-blind. Treatment assignments (active or placebo) will be blinded to the investigator, subjects and all clinical and research staff for the entire study, with the exception of designated pharmacy staff who will remain unblinded in order to dispense active drug or placebo.

The study blind will be broken upon completion of the clinical study and after the study database has been locked.

During the study, the randomization code must not be broken except in emergency situations where the identification of a subject's study treatment is required by the qualified investigator for further treatment to the subject, to assess cohort stopping rules or to complete a SAE report. Randomization information will be held by designated individual(s). When possible, the qualified investigator should discuss the emergency with the Sponsor prior to unblinding. The date and reason for breaking the blind must be recorded.

The results of the blinded safety and available PK data will be made available to the DSMB group before proceeding with the next dose level. The DSMB will be provided the randomization code to aide in the review for Part C. The bioanalytical facility will preserve the blind by reassigning alternative subject numbers to the interim data before they are made available to the PK facility and Sponsor; these alternative subject numbers will be assigned by the lab at the time of sample analysis. For the food-effect cohort (Cohort A3), the clinic will provide the lab with the meal condition for each subject, and the lab will translate this information to the corresponding alternative subject number and will provide the resulting list comprised of alternative number and associated meal condition to the PK scientist. These measures will ensure that whenever possible, the DSMB members remain blinded during their reviews and throughout the clinical part of the study. Based on review of the safety data, the DSMB may request randomization information, if necessary, to make appropriate dose escalation decisions and this unblinding will be documented.

At the request of the Sponsor, specified individuals may be unblinded and receive the randomization information prior to database lock. This unblinding will be fully documented and all unblinded individuals advised that they must not distribute randomization information to any blinded parties.

## 5.2.5. Study Drug Accountability

Complete and accurate inventory records of all study drugs will be maintained. This includes acknowledgment of receipt of each shipment of study product (quantity and condition), subject dispensing records, and returned or destroyed study product.

The labeling, storage conditions, quantity of reserve samples for the IP, and retention period of the reserve samples shall comply with the current FDA rules and regulations. Drug accountability will be performed at the completion of the trial.

Altasciences Project Number: CNO-P5-319

## 5.3. Administration of Study Drug

Study drug will be administered in the morning at approximately the same time each day. The date and time of each dose will be recorded. For each subject, all scheduled post-dose activities and assessments will be performed relative to the time of study drug administration.

Each oral dose of the assigned formulation will be administered to subjects with approximately 240 mL of water at ambient temperature. An additional volume of water of up to 150 mL may be provided in 50 mL increments to ensure that the whole dose is administered.

# 5.3.1. Part A – SAD phase with Nested Food-Effect Cohort

For Cohorts A1, A2, A4, and A5, dosing will occur following a minimum 10-hour overnight fast. Fasting will continue for at least 4 hours following drug administration, after which a standardized lunch will be served.

For Cohort A3 only, during Period 1, dosing will occur following a minimum 10-hour overnight fast. Fasting will continue for at least 4 hours following drug administration, after which a standardized lunch will be served. During Period 2, dosing will occur following a minimum 10-hour overnight fast and 30 minutes after the start of a high-fat, high-calorie breakfast. An example meal would consist of 2 eggs fried in butter, 2 strips of bacon, 2 slices of toast with butter, 4 ounces of hash brown potatoes and 8 ounces of whole milk. Substitutions in this test meal may be made provided that the meal delivers a similar number of calories from protein, carbohydrate, and fat and has comparable meal volume and texture. Subjects must eat the total content of this meal in 30 minutes or less. A standardized lunch will be served at least 4 hours after dosing.

Water will be provided as needed until at least 1 hour pre-dose. Water will be allowed beginning at least 1 hour after the administration of the drug.

### 5.3.2. Parts B and C – MAD and Smoker Phase

From Days 1 to 14, dosing will occur following a minimum 10-hour overnight fast.

On Days 1 and 14 only, fasting will continue for at least 4 hours following drug administration, after which a standardized lunch will be served. Water will be provided as needed until at least 1 hour pre-dose. Water will be allowed beginning at least 1 hour after the administration of the drug.

Meals and water will be provided at least 1-hour postdose on Days 2 to 13.

### 5.3.3. Treatment Compliance

The study drug will be dispensed only to eligible subjects and administered under the supervision of study personnel. Treatment compliance will be verified according to the site's standard operating procedures (SOPs).

#### 5.4. Meals and Fluids

Food and fluid intake other than water will be controlled for each confinement period and for all subjects. Meals and fluids will be provided at appropriate times during the confinement periods unless otherwise specified in this protocol.

Altasciences Project Number: CNO-P5-319

### **5.5.** Other Protocol Restrictions

# 5.5.1. Part A – SAD phase with Nested Food-Effect Cohort

Subjects will remain seated or kept in minimal ambulatory movement for the first 4 hours following drug administration. However, should AEs occur at any time, subjects may be placed in an appropriate position. Subjects will not engage in strenuous activity at any time during the confinement periods.

#### 5.5.2. Parts B and C-MAD and Smoker Phase

On Day 1, subjects will remain seated or kept in minimal ambulatory movement for the first 4 hours following drug administration. On Days 2 to 14, subjects will remain seated or kept in minimal ambulatory movement for the first hour following drug administration. However, should AEs occur at any time, subjects may be placed in an appropriate position. Subjects will not engage in strenuous activity at any time during the confinement periods.

Altasciences Project Number: CNO-P5-319

#### 6. STUDY PROCEDURES

Unless otherwise stated in the protocol, the SOPs of the study facilities, which are available for all activities relevant to the quality of the study, will be followed during this study. Procedure windows, including PK sample collection windows, will follow the CRU's SOPs.

An overview of the study activities for each participant is detailed in Table 1 (SAD Phase), Table 2 (MAD Phase), or Table 3 (Smoker Phase).

When safety, PK blood draws, and/or smoking assessments coincide, procedures should be carried out in the following order: (1) ECGs, (2) vital signs, (3) PK blood sampling (nominal), (4) smoking assessments.

Any deviation from protocol procedures should be noted in the source documentation and compiled for reporting in the Clinical Study Report.

## 6.1. Safety Assessments

Safety assessments will include physical examination, vital signs, 12-lead ECG, clinical laboratory tests, C-SSRS, and AE monitoring. At the discretion of an Investigator, additional safety assessments may be performed as needed to ensure subject safety.

Subjects will be admitted to the CRU, where they will be monitored to detect AEs during the study and followed appropriately to ensure resolution of AEs. An Investigator in charge will be present at the CRU for at least the first 4 hours following drug administration (on Day 1 only for the MAD Phase) and will remain available at all times throughout the study. An Advanced Cardiovascular Life Support (ACLS)-certified Safety Officer/Paramedic will be onsite 24/7, to assist Investigators with any observed AEs and the medical management of study participants. Adverse events, such as but not limited to syncope and seizures, will be managed according to standard of care. A crash cart will be available in the CRU.

#### **6.1.1.** Medical History

The medical history at Screening will include all queries by the medical and clinical staff related to the subject's well-being and history of relevant past medical events/experiences. Medical history will include all demographic data (age, sex, race, body weight, height, and BMI) and baseline characteristics. Alcohol and smoking habits will also be recorded.

Smoking history will also be collected at Screening for Part C.

## **6.1.2.** Physical Examination

A physical examination will be performed by a medically qualified and licensed individual as outlined in Table 1 (SAD Phase), Table 2 (MAD Phase) or Table 3 (Smoker Phase).

The physical examination will include a general review of the following body systems (at minimum): general appearance, head, eye, ear, nose, throat, neck/thyroid, cardiovascular, respiratory, gastrointestinal, neurological, musculoskeletal/extremities, and skin. An abbreviated physical examination may be performed at the Investigator's discretion upon admission or discharge from the clinical site.

Altasciences Project Number: CNO-P5-319

## 6.1.3. Vital Signs

Vital signs will be measured as outlined in Table 1 (SAD Phase), Table 2 (MAD Phase) or Table 3 (Smoker Phase).

Vital signs to be measured are listed below.

- Orthostatic systolic and diastolic BP and pulse rate
- Body temperature
- Respiratory rate

Blood pressure and pulse rate will be measured after the subject has been in the supine position for at least 5 minutes, repeat measurements will be taken after the subject has been standing in the upright position for at least 2 to 3 minutes (respiratory rate and temperature will be measured with blood pressure and pulse rate in the supine position only).

When vital signs are scheduled at the same time as PK blood draws, the blood draws will be obtained at the scheduled time point and the vital signs will be obtained prior to the blood draw, as close as possible to the scheduled time point.

On-study time points for vital sign measurements are presented in Table 10 (SAD Phase) and Table 11 (MAD and Smoker Phase).

Table 10 Vital Sign Recording Schedule – SAD Phase

## Vital Sign Recording - Scheduled Time Points

Upon admission (check-in)

Prior to dosing (within 60 minutes of dosing)

0.75, 1.25, 1.75, 3.75, 8, 11.75,and 23.25hours post-dose ( $\pm 15$  minutes)

Prior to discharge

End of Study/Follow-up Visit

<sup>1For the food-effect cohort, the vital signs assessments will be performed for each dosing

Altasciences Project Number: CNO-P5-319

## Table 11 Vital Sign Recording Schedule - MAD and Smoker Phase

## Vital Sign Recording - Scheduled Time Points

Upon admission (check-in)

Prior to dosing (within 60 minutes of dosing)

1.75 hours post-dose (±15 minutes) on each dosing day

3.5 hours post-dose ( $\pm 15$  minutes) on each dosing day

Prior to discharge

End of Study/Follow-up Visit

The normal range values for vital signs are as follows:

- $100 \text{ mmHg} \le \text{systolic blood pressure (BP)} \le 140 \text{ mmHg in supine position.}$
- 60 mmHg  $\leq$  diastolic BP  $\leq$  90 mmHg in supine position.
- 60 beats per minute (bpm)  $\leq$  heart rate  $\leq$  100 bpm in supine position.
- $35.5 \, ^{\circ}\text{C} \leq \text{body temperature} \leq 37.5 \, ^{\circ}\text{C}$ .
- 10 breaths per minute  $\leq$  respiratory rate  $\leq$  22 breaths per minute.
- $\geq$  20 mmHg decrease in systolic BP from supine to standing.
- $\geq$  10 mmHg decrease in diastolic BP from supine to standing.
- $\geq$  30 bpm increase in heart rate from supine to standing.

# 6.1.4. 12-Lead Electrocardiogram

Triplicate 12-lead ECG (each performed approximately 1 minute apart) will be performed as outlined in Table 1 (SAD Phase), Table 2 (MAD Phase) or Table 3 (Smoker Phase).

On-study ECG measurements are specified in Table 12 (SAD Phase) and Table 13 (MAD and Smoker Phase).

Time point applicable to Smoker Phase only.

Altasciences Project Number: CNO-P5-319

## Table 12 ECG Recording Schedule – SAD Phase

# ECG Recording - Scheduled Time Points

Upon admission (check-in)

Prior to dosing (within 60 minutes of dosing)

1, 3, 6, and 12 hours post-dose (±15 minutes)

Prior to discharge

End of Study/Follow-up Visit

## Table 13 ECG Recording Schedule – MAD and Smoker Phase

# ECG Recording - Scheduled Time Point

Upon admission (check-in)

Prior to dosing (within 60 minutes of dosing) on Day 1 only

3 hours post-dose ( $\pm 15$  minutes) on each dosing day

Prior to discharge

End of Study/Follow-up Visit

#### **6.1.5.** Laboratory Evaluations

Laboratory evaluations will be performed as outlined in Table 1 (SAD Phase), Table 2 (MAD Phase), or Table 3 (Smoker Phase).

The laboratory evaluations to be conducted for this study are presented in APPENDIX 6. Additional clinical laboratory tests may be performed by the medical laboratory as part of larger standard test panels (not required for subject safety).

An Investigator in charge or delegate will assess each abnormal value to determine if it is clinically significant. Post-dose clinically significant laboratory values will be reported as AEs, if applicable, as judged by an Investigator or delegate.

Only test results required by the protocol and/or abnormal results will be entered in the clinical database and reported in the Clinical Study Report, based on report requirement.

## 6.1.6. Columbia Suicide Severity Rating Scale (C-SSRS)

The C-SSRS is a questionnaire designed for the assessment of suicidal ideation and behavior in adolescents and adults. This will include events in the last 2 years prior to Screening.

To monitor for the emergence of suicidal ideation and behavior, subjects will undergo C-SSRS evaluations at the time points indicated in Table 1 (SAD Phase), Table 2 (MAD Phase), or Table 3 (Smoker Phase).

The questionnaire must be administered by an Investigator or other individual that is suitably qualified by education or training. See APPENDIX 7 for a sample C-SSRS (Baseline/Screening

<sup>1For the food-effect cohort, the vital signs assessments will be performed for each dosing

Altasciences Project Number: CNO-P5-319

Version) assessment and APPENDIX 8 for a sample post-dose C-SSRS (Since Last Visit Version) assessment. The Baseline/Screening Version of the C-SSRS will be used at Screening and a Since Last Visit Version will be used at all subsequent visits where the C-SSRS is administered.

On-study C-SSRS should be completed upon admission, upon discharge (each admission and discharge for Cohort A3 [Food-Effect Cohort]) and the EOS/Follow-up visit.

If a subject becomes suicidal during the study as per the results of the C-SSRS questionnaire, an Investigator should provide the appropriate treatment to the subject.

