Study Day	-28 to -2	-1	1 (Predose)	1	2	3	4	5	6	7	8	9	10	11	12	13	14	15	16	21±1
Confinement		X	X	X	X	X	X	X	X	X	X	X	X	X	X	X	X	X	X	
Ambulatory 	X																			X
Admission		X																		
Discharge																			X	
Informed Consent	X																			
Medical History	X	X																		
Demographics	X																			
Physical Examination	X	$X^3$																	$X^3$	X
Body Weight and Height (Including BMI Calculation)	X	$X^4$																		
Serology (HBsAg, HCVAb, anti-HIV 1 and 2)	X																			
Urine Drug and Alcohol Screen 	X	X																		
FSH (postmenopausal females only)	X																			
Pregnancy Test (Females Only) 	X	X																	X	X
Clinical Laboratory Test 	X	X	X			X				X							X		X	X
12-lead ECG 	X	X	X	X	X	X	X	X	X	X	X	X	X	X	X	X	X		X	X
Vital Signs 	X	X	X	X	X	X	X	X	X	X	X	X	X	X	X	X	X		X	X
Eligibility Check	X	X																		
Randomization		X																		
Study Drug Administration				X	X	X	X	X	X	X	X	X	X	X	X	X	X			
Blood Sampling for PK 			X	X	X					X				X	X	X	X	X	X	
C-SSRS Questionnaire 	X	X															X			X
M.I.N.I.	X																			
Previous and Concomitant Medication	X	X	X	X	X	X	X	X	X	X	X	X	X	X	X	X	X	X	X	X

								Ass	sess	mei	nt	Perio	d								
Visit	1	Screening	Pre	treatment								Trea	tme	nt							Follow-up/ End of Study 
Stud	y Day	-28 to -2	-1   1   (Predose)   1   2   3   4   5   6   7   8   9   10   11   12   13   14   15   16   21=										21±1								
Adve	erse Event Monitoring		X	X	X	X	K	X	X	X	X	XX	X	X	X	X	X	X	X	X	X
stimı	obreviations: BMI = body mass index; C-SSRS = Columbia-Suicide Severity Rating Scale; ECG = electrocardiogram; EOS = end of study; FSH = follicle-mulating hormone; HBsAg = hepatitis B surface antigen; HCVAb = hepatitis C virus antibody; HIV = human immunodeficiency virus; MAD = multiple cending dose; M.I.N.I. = Mini International Neuropsychiatric Interview; PK = pharmacokinetic																				
1	The timing, type, and number of safety, and PK assessments may be updated depending on emerging safety and PK data.																				
2	Subjects who discontinue the st	Subjects who discontinue the study early should complete the EOS procedures.																			
3	An abbreviated physical examination may be performed at the Investigator's discretion upon admission or discharge from the clinical site.																				

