All relevant safety and available plasma PK data will be reviewed by the DSMB before any dose escalation. The dose levels proposed for MAD cohorts may be adjusted during the course of the study based on preliminary safety and PK data. The dosing frequency may also be changed from once daily to twice daily, without changing the total daily dose outlined in the protocol.

The MAD phase will have a maximum of 4 cohorts. The number of cohorts may be changed at the discretion of the Sponsor depending on the emerging safety and PK data from the previous cohorts. The increase from one dose level to the next dose level will not be more than 3-fold. A MAD daily dose level cannot be higher than the highest dose level tested in SAD.

Subjects will be confined to the CRU from at least 10 hours prior to drug administration until approximately 48 hours after last study drug administration. Subjects will therefore be confined for 17 days and 16 nights (Day -1 to Day 16).

Subjects will return for a follow-up visit approximately 5 days after the last PK blood sample/discharge (Day 21±1).

The schedule of activities of the MAD Phase of the study is described in Table 2.

Altasciences Project Number: CNO-P5-319

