## 3.5.1. Individual Subject Stopping Rules

Participation in the clinical study may be discontinued by the Principal Investigator or by the Sponsor for any of the following reasons, but not limited to:

- Any subject experiencing a confirmed drug-related moderate or severe AE or serious AE (SAE) will not receive the next scheduled dose of IP until a safety review of the AE is performed by an Investigator and Sponsor Medical Monitor. The decision to continue dosing must be agreed upon by both an Investigator and Sponsor Medical Monitor.
- Any subject experiencing seizures, intractable headaches, or suicidal ideations.
- Liver chemistry elevations that meet any of the following parameters:
  - ALT or AST  $> 3 \times$  upper limit of normal (ULN) and total bilirubin  $> 2 \times$  ULN without elevated alkaline phosphatase.
  - ALT or AST > 3 × ULN with appearance of fatigue, nausea, vomiting, right upper quadrant pain or tenderness, fever, rash, and/or eosinophilia (>5%).
  - ALT or AST > 8 × ULN, which is confirmed.
- Meets either of the following ECG criteria:
  - QTcF >500 ms
  - QTcF change from baseline >60 ms
  - Subject non-compliance (including any violation of protocol requirements which may affect the study outcome)

Altasciences Project Number: CNO-P5-319

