## 6.4.6. Minnesota Nicotine Withdrawal Scale (MNWS)

The Minnesota Nicotine Withdrawal Scale (MNWS) is a self-report measure used to monitor symptoms of tobacco withdrawal. The MNWS will be administered by an Investigator or other individual that is suitably qualified by education or training on Day -1 and at 5 hours (±30 minutes) postdose on Days 1 to 14 as outlined in Table 3. The assessment on Day -1 should be completed at approximately the same time as the 5-hour postdose timepoint on dosing days. See APPENDIX 11 for a MNWS example.

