# Minnesota Nicotine Withdrawal Scale

Fill in the a	appropriate (	circle that c	orresponds	
0 = None	1 = Slight	2 = Mild	3 = Moderate	4 = Severe

Symptoms	0	1	2	3	4
1. Desire/ cravings					
2. Anger/ irritability/ frustration					
3. Anxiety/ nervousness					
4. Difficulty concentrating					
5. Restlessness					
6. Insomnia/ sleep problems/ waking at night					
7. Increased appetite/ weight gain					
8. Depressed mood					
9. Constipation					
10. Coughing					
11. Decreased pleasure from events					
12. Dizziness	0				
13. Drowsy					
14. Impatient					
15. Impulsive	0				

Staff Initi	Staff Initials: Time completed:								
Once the subject has completed and initialed the question	nnaire.								
			Subject	Initials:					
15. Impulsive									
14. Impatient									
20.0.00									

Altasciences Project Number: CNO-P5-319

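### In Parts B and C no C-SSRS is scheduled between Day -1 and Day 14, so the first form that can show treatment-emergent ideation comes with at most 1 of 14 once-daily doses left

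*Protocol*

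**What the plan says.** Protocol 6.1.6 gives the aim and refers to the schedule tables for timing: "To monitor for the emergence of suicidal ideation and behavior, subjects will undergo C-SSRS evaluations at the time points indicated". It then adds "On-study C-SSRS should be completed upon admission, upon discharge", plus the follow-up visit. SAP 8.6 repeats both statements.

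In Tables 2 (Part B) and 3 (Part C), the row "C-SSRS Questionnaire" is marked at Screening, Day -1, Day 14 and Day 21±1. Study drug is marked on Days 1 to 14. Discharge is marked on Day 16, which agrees with the confinement period in 3.3.2 and 3.3.3. The Day 14 form has no clock time. In Part A the tables and text agree, because Table 1 marks the form on Day 3, the discharge day.

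Section 3.5.1 lists reasons for which a subject's participation may be discontinued, among them: "Any subject experiencing seizures, intractable headaches, or suicidal ideations".

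Other provisions bear on detection:
- Adverse event monitoring is marked daily (Tables 2 and 3), and 7.4 describes how events are recorded.
- Section 6.1 allows further safety assessments at the Investigator's discretion.
- Footnote 1 of Table 2 (and of Table 3) says: "The timing, type, and number of safety, and PK assessments may be updated depending on emerging safety and PK data".
- In Part C only, the MNWS is given daily on Days 1 to 14. It includes the item "8. Depressed mood", but 6.4.6 says it "is a self-report measure used to monitor symptoms of tobacco withdrawal".

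**The concern.** SBP-9330 acts on the central nervous system and has not been given to humans before. Section 1.4 names the C-SSRS among the practices relied on to protect subjects. An instrument meant to monitor emergence, tied to a reason for discontinuing a subject, is most useful if it is asked while doses remain to be withheld. Here the only form between admission and the end of dosing falls on the last dosing day, and the text allows a reading that puts it two days later.

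What is at stake is narrow: a scheduled direct question about ideation during the dosing course. The Day 14 and Day 16 wording matters separately but less. If the only in-house form is completed before the Day 14 dose, no C-SSRS follows the last dose until Day 21±1. The DSMB's minimum data set before escalation (3.2) runs only to discharge, so it would then contain no C-SSRS from after the final dose.

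**Working it through.** The plan states no figure on this point, so there is none to reproduce. The check is a count of doses still to come when each form is answered.

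**Inputs**
- Doses: 14, once daily on Days 1 to 14 (3.3.2, 3.3.3).
- C-SSRS days in Parts B and C: Screening, -1, 14, 21±1 (Tables 2 and 3, read by column position). As a check, the laboratory row of Table 2 read the same way gives Days 3, 7, 14, 16 and 21 after dosing starts, which matches its footnote 7.
- Discharge: Day 16.
- Cohorts of 10: 3 planned and at most 4 in Part B; 2 planned and at most 3 in Part C.

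**Doses remaining, once daily**

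A form completed before the dose on day d leaves 14 − d + 1 doses. A form completed after it leaves 14 − d.

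| Form | Doses remaining of 14 |
|---|---|
| Day 14, pre-dose | 14 − 14 + 1 = 1 |
| Day 14, post-dose | 14 − 14 = 0 |
| Day 16, discharge | 0 (dosing ended on Day 14) |
| Day 7, pre-dose (proposed) | 14 − 7 + 1 = 8 |
| Day 7, post-dose | 14 − 7 = 7 |

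The Day -1 form precedes all 14 doses, but it cannot show ideation that arises on treatment, so it is not counted.

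**Twice daily**

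Section 3.3.2 and Table 6 permit a change to twice-daily dosing. The total is then 14 × 2 = 28 doses. A form before the first Day 14 dose leaves 1 × 2 = 2. A form before the first Day 7 dose leaves 8 × 2 = 16.

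**Reach of a Day 7 form**

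It follows the doses of Days 1 to 6. The figure of 8 applies only to ideation already present when the form is completed. For later onset the limit stays at 1 (Day 14 form kept, pre-dose) or 0 (Day 16 form only).

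**Number of forms**

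The blind means active and placebo subjects must all complete the form.
- Subjects: planned 3 × 10 + 2 × 10 = 50; maximum 4 × 10 + 3 × 10 = 70.
- Day 7 added and Day 14 moved to Day 16: one more than the tables show, so 50 extra forms (maximum 70).
- Days 7, 14 and 16 all used: two more than the tables show, so 100 extra forms (maximum 140).

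Replacement of withdrawn subjects (5.2.3) would add to these.

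**The case against.** The strongest case against is that the plan already covers the risk and that a Day 7 form is a matter of preference. Exclusion criteria 9, 11 and 12 remove psychiatric disease, a history of ideation or behaviour on the C-SSRS, and disorders found on the M.I.N.I. Subjects are confined throughout dosing, with daily adverse event monitoring, medical cover and discretionary assessments. Section 3.5.1 acts on ideation however it is found. The nonclinical summary reports no adverse effect on the nervous system of conscious rats. The Investigator's Brochure and the Data and Safety Monitoring Plan are not available here, so the level of risk cannot be judged from them. Day 7 is also not unique: a Day 3 pre-dose laboratory assessment exists too.

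Much of this stands, and it rules out several stronger readings:
- A reader might infer that ideation during dosing would go unnoticed. The documents do not support that, because several routes could bring it to light. None of them, however, is a scheduled direct question about ideation. Section 7.4 specifies open-ended health questions at the start of each study period and before departure, and the MNWS is a withdrawal scale absent from Part B.
- A reader might infer that endpoint data are lost. They are not, because the since-last-visit form reaches back over the interval.
- A reader might infer that the text and tables contradict each other outright. Section 6.1.6 can be read together with the tables as requiring both Day 14 and Day 16, so this is a minor alignment.
- A reader might want an expected number of doses saved. The documents give neither incidence nor onset timing, so no such average can be supported.

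On the choice of day, a Day 3 pre-dose form would leave 14 − 3 + 1 = 12 doses, but could catch only ideation present after two doses. Day 7 is a judgement that splits the dosing course near its middle and uses an existing assessment.

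**Conclusion.** The point holds as a modest safety improvement. In Parts B and C the first scheduled C-SSRS that can show treatment-emergent ideation comes with 1 of 14 doses left if it is done before the Day 14 dose. It comes with none left if it is done after that dose or at Day 16 discharge. Under twice-daily dosing the limit is 2 of 28. A Day 7 pre-dose form would raise the once-daily figure to up to 8 of 14.

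These are upper limits on doses that a scheduled answer could lead to withholding. They assume that ideation is present at the form and disclosed on it, and that the discretion in 3.5.1 is used. They do not estimate how many subjects would be affected. The primary endpoint stands as planned. The unmarked Day 16 form and the unstated Day 14 timing are clerical, but worth settling in the same edit.

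**What to change.** 1. In Tables 2 and 3, add one since-last-visit C-SSRS to the Day 7 pre-dose assessments, where laboratory and PK samples are already taken.
2. Mark the Day 16 discharge form that 6.1.6 already calls for, so that one in-house form follows the last dose.
3. If the Day 14 form is kept, state that it is completed before the dose.
4. Align 6.1.6, SAP 8.6 and SAP Tables 14 and 15 with the result. The columns of those two SAP tables do not line up in the available text, so their day positions should be checked when this is done.

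Section 3.5.1 needs no change.

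The cost is one or two short forms per subject beyond those the tables mark: 50 to 100 as planned, and up to 140 if all optional cohorts are run, before replacements. If Days 14 and 16 are both taken as already required, only the Day 7 form is new. Subjects are in house, and the questionnaire and qualified raters are already in use. The downside is the added burden, with no gain for ideation that begins after the Day 7 form.
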